2.2.2 Secondary Objective

- To assess the effect of L-citrulline administration on urinary nitric oxide metabolite (nitrite/nitrate) levels in patients at high risk of developing BPD-PH

3. Study Population

3.1 Age of Participants:

32 +/- 1 week postmenstrual age

3.2 Sample Size:

28 participants: 10* participants for pharmacokinetic profile characterization and 18 participants for evaluating the tolerability and ability to achieve target trough plasma levels

- Group 1: 5 participants
- Group 2: 5 participants
- Group 3: 18 participants

* Note that the total participant size for Groups 1 and 2 has been reduced from the originally proposed total of 18 participants to 10 participants. This change was made based on the single patient PK analysis on the 10 enrolled participants. This analysis was assessed to be sufficient to perform the population PK modeling needed to design the next phase of the study. Both the DSMB and the FDA approved the change in participant size.

3.3 Inclusion Criteria:

1. Infants born prematurely at \leq 28 weeks gestation requiring invasive (mechanical ventilation) or non-invasive positive pressure support (nasal continuous positive airway pressure, high flow nasal cannula \geq 1 lpm) at 32 +/- 1 weeks postmenstrual age
2. Tolerating at least one-half of full volume oral/gavage tube feedings (using 120 ml/kg/d as full volume oral/gavage tube feedings)
3. The continuous need for some form of respiratory support (supplemental oxygen and/or flow, or mechanical ventilation) for the prior 14 days
4. Hemoglobin \geq 10 mg/dL

3.4 Exclusion Criteria:

1. Known major fetal anomaly or chromosomal aneuploidy
2. Clinical evidence of congenital heart disease (except patent ductus arteriosus, atrial septal defect, or ventricular septal defect [PDA, ASD, VSD])
3. Urine output < 1 ml/kg/hr
4. History of or known to have liver failure
5. History of or known to have necrotizing enterocolitis
6. History of or known to have significant feeding intolerance beyond the first week of life
7. Presence of any acute illness defined by fever >100.4F, vomiting, or diarrhea
8. Hemoglobin < 10 mg/dL
9. NICU cases determined to be futile (anticipated death prior to hospital discharge)
10. Multiple births

4. Design

Study to Assess Pharmacokinetics of L-Citrulline in infants at high risk of developing pulmonary hypertension associated with Bronchopulmonary Dysplasia

5. Study Procedures

5.1 Recruitment/Participant Identification Process:

Participants will be recruited while they are hospitalized at the Neonatal Intensive Care Nursery either at Primary Children's Hospital or University of Utah Hospital or Intermountain Medical Center Hospital. The study team will review patient medical records to determine eligibility.

5.2 Informed Consent:

5.2.1 Description of location(s) where consent will be obtained:

University of Utah Hospital Neonatal Intensive Care Nursery
Primary Children's Hospital Neonatal Intensive Care Nursery
Intermountain Medical Center Neonatal Intensive Care Nursery

5.2.2 Description of the consent process(es), including the timing of consent:

Parents/guardians with children fitting the eligibility criteria will be approached by the PI or study coordinator and introduced to the study. During that time the study procedures and participant involvement will be thoroughly discussed, questions encouraged, and full understanding of the protocol ensured. Parents/guardians will be encouraged to take the consent form home to discuss with others before making any decision to sign the consent form. Consent from the parent/guardian and assent if

applicable will be obtained before any L-citrulline will be administered and before any sample will be collected.

5.3 Procedures:

Consent from the parent/guardian will be obtained.

The study drug, L-citrulline, will be provided by Asklepiion Pharmaceuticals.

5.3.1 Single-dose pharmacokinetic studies: Participants will be enrolled into the two groups, Group 1 (which will consist of 5 participants) and Group 2 (which will consist of 5 participants) in an alternating basis. Both Group 1 and Group 2 participants will receive a single, 150 mg/kg dose of oral L-citrulline. The L-citrulline will be provided by Asklepiion Pharmaceuticals. The L-citrulline will be procured in powder form and will be solubilized in sterile water to achieve a concentration of 50 mg/ml. Therefore, 3 ml/kg of the solubilized L-citrulline (50 mg/ml) will be administered to the participant.

To assess pharmacokinetic parameters, the study team will collect three, 0.3-1.0 ml blood draws (whole blood) from infants who receive the single dose of 150 mg/kg oral L-citrulline. Blood sampling volumes will be limited to a maximum of 1 ml/kg total over a 24-48 hour period. If the participant is not nipple feeding, the dose will be delivered via the participant's indwelling gavage feeding tube.

- For Group 1: one blood draw will be pre-dose and 2 blood draws will be post-dose. The pre-dose blood draw will occur 24-48 hours prior to administering the dose of oral L-citrulline and the two post-dose draws will occur at 1 hours (+/- 10 minutes) and 2.5 hours (+/- 10 minutes) post-dose.
- For group 2: one blood draw will be pre-dose and 2 blood draws will be post-dose. The pre-dose blood draw will occur 24-48 hours prior to administering the dose of oral L-citrulline and the two post-dose draws will occur at 15 minutes (+/- 10 minutes) and 3 hours (+/- 10 minutes) post-dose

These sampling times are designed to estimate the population PK parameters of a typical infant using scaling and population PK analysis of available oral PK profiles in adults (28).

The single dose pharmacokinetic studies have been completed. PK data from 10 subjects (5 in group 1 and 5 in group 2) were analyzed and assessed as being sufficient to provide the information needed to design the next phase, the steady state pharmacokinetic studies.

5.3.2 Steady-state pharmacokinetic studies:

To evaluate the tolerability and ability to achieve target trough L-citrulline levels of 50-80 μ M, an additional group of 18 infants (group 3) will be given oral L-citrulline doses at intervals over a total of 72 hours. The L-citrulline will be provided by Asklepiion Pharmaceuticals. If the participant is not nipple feeding, the dose will be

delivered via the participant's indwelling gavage feeding tube. The dose and interval of L-citrulline are based on results from the studies that assessed pharmacokinetic parameters using a maximum daily dose of 3 g/kg/d. The choice of the maximum daily dose is based on a recent study that showed good tolerability and reported no adverse effects in children with mitochondrial encephalomyopathy, lactic acidosis and stroke-like episodes (MELAS syndrome) treated with oral l-citrulline at a dose of 3 g/kg/d (500 mg/kg/dose given every 4 hours) (37).

Based on results from the single dose pharmacokinetic studies, the infants in group 3 will be given oral L-citrulline doses of 60 mg/kg every 6 hours +/- 30 minutes (4 times a day) for 72 hours (total of 12 doses). This is a total daily dose of 240 mg/kg/day.

The L-citrulline will be provided by Asklepiion Pharmaceuticals. The L-citrulline will be procured in powder form and will be solubilized in sterile water to achieve a concentration of 50 mg/ml. Therefore, 1.2 ml/kg of solubilized L-citrulline (50 mg/ml) will be administered to the participant every 6 hours +/- 30 minutes (4 times a day) for 72 hours. This is a total daily volume of 4.8 ml/kg/day.

For group 3, the study will collect two, 0.3-1.0 ml blood draws (whole blood) and two, 1 ml urine samples. Blood sampling volumes will be limited to a maximum of 1 ml/kg total over a 24 hour period. One blood draw will occur between 10 minutes and 6 hours prior to administering the first dose of oral L-citrulline and the second blood draw will occur 10 to 30 minutes prior to administering the last dose of oral L-citrulline. These sampling times are designed to assess baseline and trough L-citrulline plasma levels. One urine sample will be collected on the day prior to administering the first dose of oral L-citrulline and the second urine sample will be collected between 4 and 8 hours following the last dose of oral L-citrulline. These urine collection times are designed to assess baseline levels of nitric oxide metabolites (nitrite/nitrate) in the urine and assess whether there is an increase in levels of nitric oxide metabolites in the urine in response to 72 hours of L-citrulline dosing.

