5.3.6 Participant monitoring

All participants will be monitored for clinical evidence of necrotizing enterocolitis, gastrointestinal bleeding, sepsis, feeding intolerance (including vomiting and diarrhea), electrolyte disturbances, hemodynamics, alteration of hematological parameters and death. Any electrolytes, hematologic laboratories, and eye examinations that are ordered as part of standard of care by the participants clinical care team will be monitored. Hypotensive subjects (defined as a decrease in mean arterial blood pressure of more than 25% baseline) will be treated with pharmacological/volume supplementation interventions at the discretion of the attending physician. Treatment unresponsive hypotensive subjects will be withdrawn from the study. Subjects who develop significant feeding intolerance will be withdrawn from the study. Infants who are made NPO for a time period long enough that they miss any doses of L-citrulline will be withdrawn from the study.

6. Statistical Methods, Data Analysis and Interpretation

After the first 3 participants are enrolled in the single-dose PK study (3 participants enrolled in either Group 1 or Group 2), and after the first 3 participants are enrolled in the steady-state pharmacokinetic study (3 participants enrolled in Group 3), an initial PK analysis will be performed and the data will be reviewed by the DSMB to assess for safety to continue the single dose PK study and to continue the steady-state pharmacokinetic study.

Throughout the study, participants who are withdrawn from treatment due to adverse events will be replaced for PK analysis.

Data collected from this study will be examined to ensure that all participants in the analysis meet inclusion criteria. Summary statistical analysis will be conducted to describe participant demographics, citrulline dosing, and participant PK profiles. Outliers in the measured citrulline levels that may influence the estimation of PK parameters will be evaluated. A population model will be developed to describe the citrulline PK and population variability.

The non-linear mixed effect modeling software NONMEM® version 7.3.0 (ICON Development Solutions, [name], USA) will be used to develop models. Perl-speaks-

NONMEM (PsN) 4.4.0, Pirana 2.9.0, and R packages (version 3.2.1) will be used to facilitate, evaluate, and visualize the model development.

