7.4.4 Deviation Reporting

A **deviation** is ANY departure from the defined procedures and treatment plans as outlined in the protocol version or application version submitted and previously approved by the Institutional Review Board (IRB). Deviations have the potential to place participants at risk and can also undermine the scientific integrity of the study thus jeopardizing the justification for the research.

Deviations are *unplanned* and/or *unintentional* events. Any changes in the IRB-approved research protocol should not be initiated without submission of an amendment for IRB review and approval. If such changes are initiated before IRB approval for the change is given, a deviation has occurred.

Criteria for Reporting Deviations

The University of Utah IRB requires researchers to submit deviations that meet **one or more** of the following criteria:

- **Intended to eliminate apparent immediate hazard** to a research participant (such as changing the dose of a medication due to possible toxicity);
or
- **Caused possible harm** to participants or others, or places them at increased risk of harm - including physical, psychological, economic, or social harm, such as a breach of confidentiality;
or

- **Possible serious or continued non-compliance** (such as a deviation that has happened previously and is now being repeated).
 - **Serious non-compliance** is an act or omission to act that resulted in significant harm (physical, psychological, safety, or privacy) or significantly increased the possibility of harm to the rights and welfare of research participants.
 - **Continuing non-compliance** is a pattern of repeated actions or omissions to act that suggests a future likelihood of reoccurrence and that indicates a deficiency in the ability or willingness to comply with Federal regulations, VHA Handbooks or the policy, requirements, and determinations of the IRB governing human subject research.

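### Both hemoglobin eligibility criteria give the cut-off in mg/dL, so the rule as written excludes no infant

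*Combined protocol and SAP*

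**What the plan says.** Section 3.3 (Inclusion Criteria), item 4 requires "Hemoglobin \geq 10 mg/dL". Section 3.4 (Exclusion Criteria), item 8 removes infants with "Hemoglobin < 10 mg/dL". Number and unit are the same in both, and the two items are exact complements, so they work as a single rule.

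Three other places rely on the eligibility text:

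- Section 5.1 on screening: "The study team will review patient medical records to determine eligibility".
- Section 6 on the analysis: "Data collected from this study will be examined to ensure that all participants in the analysis meet inclusion criteria".
- Section 7.4.4, which defines a deviation as "ANY departure from the defined procedures and treatment plans as outlined in the protocol version", or in the application version that the IRB approved.

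Section 5.3.6 provides for monitoring of hematological parameters and of blood tests ordered in routine care, but sets no hemoglobin limit.

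**The concern.** A cut-off of 10 mg/dL lies far below any hemoglobin an infant could plausibly have. A criterion written as both an inclusion and an exclusion item is evidently meant to separate some infants from others. As printed, it separates none.

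What is at stake is eligibility. The infants concerned are described in section 3.3 as "Infants born prematurely at \leq 28 weeks gestation requiring invasive (mechanical ventilation) or non-invasive positive pressure support", and they give research blood samples. This is the only hemoglobin rule at entry. If the text is taken at its word, an infant with low hemoglobin passes screening and also passes the section 6 check of analysed participants. Measured against the protocol wording, enrolling that infant would not be a departure either. If staff instead apply the number in g/dL, they apply a rule that the approved protocol does not state, and screening practice differs from the standard against which it would be audited.

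**Working it through.** The plan derives nothing here, so there is no calculated figure to reproduce. The check is a unit conversion followed by applying the rule as printed.

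**Inputs**

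- Inclusion cut-off: at least 10 mg/dL (section 3.3, item 4).
- Exclusion cut-off: below 10 mg/dL (section 3.4, item 8).
- Planned participants: 5 in Group 1, 5 in Group 2 and 18 in Group 3 (section 3.2).
- Hemoglobin range: not given in the documents. Assumed here to be 1 to 20 g/dL, deliberately wide at the low end.

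**Conversion** (1 g = 1000 mg)

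- Printed cut-off: 10 mg/dL ÷ 1000 = 0.01 g/dL.
- The same number in g/dL: 10 g/dL × 1000 = 10,000 mg/dL.
- Ratio: 10,000 ÷ 10 = 1000.

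**Applying the printed rule over the assumed range**

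| Hemoglobin (g/dL) | In mg/dL | Multiple of 10 mg/dL | Excluded as printed? | Excluded if the unit were g/dL? |
|---|---|---|---|---|
| 1 | 1,000 | 100 | no | yes |
| 3 | 3,000 | 300 | no | yes |
| 5 | 5,000 | 500 | no | yes |
| 8 | 8,000 | 800 | no | yes |
| 10 | 10,000 | 1,000 | no | no |
| 15 | 15,000 | 1,500 | no | no |
| 20 | 20,000 | 2,000 | no | no |

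As printed, the rule gives the same answer in every row. With the number kept and the unit read as g/dL, it would divide the range. The last column only shows the size of the discrepancy; it does not establish what the sponsor intended.

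**Can another part of the document correct it?** No. The two items carry the same unit, so neither corrects the other. Section 5.3.6 names hematological monitoring without a limit, and no other section gives a hemoglobin value. The identical unit in two separate lists also makes a text-extraction fault unlikely.

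**Reach:** 5 + 5 + 18 = 28 planned infants come under the criterion. Section 5.3.1 reports the first 10 as completed, so a correction can change screening only for Group 3 infants not yet enrolled, at most 18 plus any replacements.

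**The case against.** The strongest reply is that this is an obvious slip with little practical effect. Eligibility is decided by a study team reading neonatal intensive care records, and such readers are unlikely to apply 0.01 g/dL. The paired wording itself shows that a working cut-off was intended, and the section 6 check fails only if the person making it takes the unit literally. This largely stands: nothing in the documents shows that any infant was wrongly enrolled, and the practical effect is probably small.

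The deviation argument is also open to challenge. Section 7.4.4 refers to the IRB application as an alternative standard. We cannot see that application, and it may state the unit correctly. The definition speaks of procedures and treatment plans and does not name eligibility. That stands too, so the point about deviations holds only against the protocol's own wording.

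Other safeguards do not depend on this criterion. Sections 5.3.1 and 5.3.2 cap the blood volume drawn, and section 5.3.6 covers hematological monitoring.

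These points reduce the weight of the error but do not remove it. Both items remain wrong as written. Section 7.4.4 itself says that changes to the approved protocol should go through an amendment, which is a reason not to leave the correction to each reader.

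**Conclusion.** The concern holds. The only hemoglobin rule at entry is printed with a cut-off of 0.01 g/dL, a factor of 1000 below the same number in g/dL. Followed literally, it excludes no infant.

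The conversion needs no assumption. The statement that nobody is excluded rests on the assumed range of 1 to 20 g/dL, but any hemoglobin of 0.01 g/dL or more gives the same result, so the choice of range is immaterial. The factor of 1000 compares units for the same number and does not presume which threshold the sponsor meant.

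The consequence is confined to eligibility and to the checks made against it. It does not touch the population pharmacokinetic model, the sample size or any endpoint. It should be corrected because it is an operative threshold, although it is unlikely to have affected results.

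**What to change.** The sponsor should confirm the intended unit and threshold, then correct section 3.3, item 4 and section 3.4, item 8 in the same amendment so that they remain complements. If the IRB application or the screening forms carry the same unit, they should be brought into line at the same time.

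The cost is one unit in each of two lines at the next amendment. As an option, the study team can confirm from existing screening records that infants already enrolled met the intended criterion. That covers the 10 single-dose infants and whatever part of Group 3 has been enrolled (18 planned, plus replacements), and needs no new data collection.

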5.3.3 Blood Samples

Blood samples will be processed and the plasma harvested into labeled tubes which are stored in a designated freezer section at -80 degrees C, where they will be collected by study personnel. For each of the blood samples we will test for plasma citrulline and arginine levels. Analysis will be done by ARUP.

5.3.4 Urine samples

Each 1 ml urine samples will be aliquoted into 2 separate tubes (0.5 ml urine per tube), then stored in a designated freezer section at -80 degrees C, where they will be collected by study personnel. One of the aliquoted urine samples will be tested for NO metabolites (nitrites/nitrates) and the second aliquoted urine sample will be tested for Cr (to normalize the sample). Urine nitrite/nitrate analysis will be done in [name] laboratory. Urine Cr analysis will be done by ARUP.

5.3.5 Additional data

Additional data collected will include demographics; vital signs including weight, length, heart rate, respiratory rate, temperature, and blood pressure; dietary/nutrition information; concomitant medications. For the Group 1 and Group 2 participants (single dose PK studies), the blood pressure will be monitored at least 3 times after the participant receives the study drug. For the Group 3 participants (steady state PK studies), the blood pressure will be monitored at least 4 times daily for 4 days (72 hours when the participant is receiving the study drug and 12 hours after last dose). The heart rate, respiratory rate, temperature, and blood pressure will be monitored for 12 hours following the last dose of L-citrulline.

5.3.6 Participant monitoring

All participants will be monitored for clinical evidence of necrotizing enterocolitis, gastrointestinal bleeding, sepsis, feeding intolerance (including vomiting and diarrhea), electrolyte disturbances, hemodynamics, alteration of hematological parameters and death. Any electrolytes, hematologic laboratories, and eye examinations that are ordered as part of standard of care by the participants clinical care team will be monitored. Hypotensive subjects (defined as a decrease in mean arterial blood pressure of more than 25% baseline) will be treated with pharmacological/volume supplementation interventions at the discretion of the attending physician. Treatment unresponsive hypotensive subjects will be withdrawn from the study. Subjects who develop significant feeding intolerance will be withdrawn from the study. Infants who are made NPO for a time period long enough that they miss any doses of L-citrulline will be withdrawn from the study.

6. Statistical Methods, Data Analysis and Interpretation

After the first 3 participants are enrolled in the single-dose PK study (3 participants enrolled in either Group 1 or Group 2), and after the first 3 participants are enrolled in the steady-state pharmacokinetic study (3 participants enrolled in Group 3), an initial PK analysis will be performed and the data will be reviewed by the DSMB to assess for safety to continue the single dose PK study and to continue the steady-state pharmacokinetic study.

Throughout the study, participants who are withdrawn from treatment due to adverse events will be replaced for PK analysis.

Data collected from this study will be examined to ensure that all participants in the analysis meet inclusion criteria. Summary statistical analysis will be conducted to describe participant demographics, citrulline dosing, and participant PK profiles. Outliers in the measured citrulline levels that may influence the estimation of PK parameters will be evaluated. A population model will be developed to describe the citrulline PK and population variability.

The non-linear mixed effect modeling software NONMEM® version 7.3.0 (ICON Development Solutions, [name], USA) will be used to develop models. Perl-speaks-

NONMEM (PsN) 4.4.0, Pirana 2.9.0, and R packages (version 3.2.1) will be used to facilitate, evaluate, and visualize the model development.

The model development process would include two major steps: base model structure evaluation and covariate screening. The development of a base structural model will include the evaluation of compartment numbers, baseline effects, absorption and elimination kinetics. The stochastic models describing between-subject variability in PK parameters and intra-subject variability in observations will be also examined.

Potential covariates that are predictive of citrulline PK variability will be screened using the stepwise covariate model (scm) building tool of PsN. The continuous covariates to be examined will include, but not be limited to, body weight, length, postnatal age, gestational age, etc. Categorical covariates to be examined will include, but not be limited to, sex, race, ethnicity, and concomitant medication (yes/no). The predefined parameter-covariate association for continuous covariates will be included as a power relation, while categorical covariates will be linearly included. Both stepwise forward selection and backward elimination will be incorporated for covariate searching. Changes in OFV will be considered significant at $p<0.05$ (χ^2 -distribution, 1 df, Δ OFV > 3.84) during forward selection, and $p<0.01$ (1 df, Δ OFV > 6.63) during backward elimination. In addition to the aforementioned statistical criteria, the following standard diagnostic plots will also be used to visually assess the final covariate model fit: observed concentrations versus population- and individual-predicted concentrations, conditional weighted residuals versus time and population-predicted concentrations. To assess the model stability, a nonparametric bootstrap analysis will be conducted. The visual predictive check (VPC) will be performed to further evaluate the final model performance.

Once the final population PK model is determined, an optimal dosing plan will be developed using the model to achieve target plasma trough concentrations of 50-80 μ M in patients at high risk of developing BPD-PH. Statistical comparison between actual trough concentrations and model predicted concentrations will be conducted. Model prediction capability will be evaluated and refinement will be performed.

The final population PK model has been determined and the optimal dosing plan has been developed to target plasma trough concentrations of 50-80 μ M (trough plasma concentrations that are based on data from the single dose PK study and that are appropriate for infants in this study). The optimal dosing plan is to give oral L-citrulline doses of 60 mg/kg every 6 hours +/- 30 minutes (4 times a day) for 72 hours (total of 12 doses). This is a total daily dose of 240 mg/kg/day.

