1.6 Hypothesis, what is being proposed, and value provided

The hypothesis is that oral L-citrulline will be well tolerated, without significant adverse effects in infants at high risk of developing pulmonary hypertension (PH) associated with BPD. We propose to first characterize the PK profile of oral L-citrulline in order to define an appropriate dose range and treatment interval for infants at high risk of developing BPD-PH. Then using the doses and intervals generated by the PK profile, with a maximum dose of 3 g/kg/d (37), we propose to evaluate the tolerability and ability to achieve the target trough L-citrulline plasma level of approx. 50-80 μ M in patients at high risk of developing BPD-PH treated for 72 hours with oral L-citrulline. These studies will provide the data needed to design a full-scale randomized multi-center trial to evaluate the efficacy of oral L-citrulline therapy to ameliorate BPD-PH in human infants, a patient population that has a desperate need of new therapies.

2. Purpose and Objectives

2.1 Specific Goals of this Proposal:

The goal is to develop oral L-citrulline clinically for the treatment of pediatric pulmonary hypertension associated with bronchopulmonary dysplasia (BPD-PH); before pursuing a large scale treatment trial, pharmacokinetic dose-finding, tolerability studies in patients at high risk of developing BPD-PH are warranted.

2.2 Objectives:

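### Gestational and postnatal age are strongly collinear by the entry rule yet compete in one stepwise screen, and body weight must pass the same screen although dosing is per kg

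*Combined protocol and SAP*

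**What the plan says.** Section 6 describes a stepwise covariate search for the population PK model. On candidates it says "The continuous covariates to be examined will include, but not be limited to, body weight, length, postnatal age, gestational age, etc". On form: "The predefined parameter-covariate association for continuous covariates will be included as a power relation". On selection: "Both stepwise forward selection and backward elimination will be incorporated for covariate searching", with a drop in objective function above 3.84 to enter and 6.63 to stay (1 df each).

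Section 3.1 gives the age of participants as "32 +/- 1 week postmenstrual age". Section 3.3 limits birth to 28 weeks' gestation or less, with no lower limit. No mean or spread of gestational age is given. There is no rule for collinear covariates and no choice between the two ages.

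Section 6 also says that the final model has been determined and yields 60 mg/kg every 6 hours, with no age term. It separately plans a comparison of observed and predicted troughs, followed by refinement of the model. Section 1.6 gives the purpose as supplying data to "design a full-scale randomized multi-center trial to evaluate the efficacy" of the treatment.

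**The concern.** Postmenstrual age is gestational age at birth plus postnatal age. An entry rule that holds the sum within a narrow band makes one age rise as the other falls. Two covariates that fit nearly equally well inside the band then compete on a p-value in 10 to 28 infants.

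The label matters outside the band. A postnatal-age effect says that an infant's clearance changes as the infant grows older. A gestational-age effect is fixed at birth and predicts no such change. Section 1.5 speaks of long-term treatment, so a later trial may well follow infants past 33 weeks, although the documents do not state its age range.

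Body weight stands in the same list. The regimen is per kg, which presumes that weight matters, yet the model keeps weight only if it passes the screen against correlated size and age variables.

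**Working it through.** **Cut-offs.** The chi-square quantiles with 1 df are 3.841 (p = 0.05) and 6.635 (p = 0.01), so the plan's 3.84 and 6.63 are reproduced.

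**Correlation.** Inputs: entry window (Section 3.1), upper gestational limit (Section 3.3), and an assumed even spread of both ages, independent of each other. With gestational range *a* and postmenstrual range *b* in weeks, r = -a/√(a² + b²), and the variance inflation is 1 + a²/b².

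| Assumed gestational range | Literal window, 31-33 (b = 2) | Completed weeks, 31w0d-33w6d (b = 20/7 = 2.857) |
|---|---|---|
| 25-28 (a = 3) | -3/√13 = -0.83; inflation 3.3 | -3/√17.16 = -0.72; inflation 2.1 |
| 22-28 (a = 6) | -6/√40 = -0.95; inflation 10 | -6/√44.16 = -0.90; inflation 5.4 |

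For 23-28 weeks and the literal window, r = -5/√29 = -0.93. On the log scale, which the power relation uses, it is slightly weaker (-0.915).

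**Which age is kept.** This is a simulation with a regression stand-in. One age truly acts on log clearance as a power effect; the change in objective function is -n·ln(1 - R²); the better-fitting age enters above 3.84 and stays above 6.63. Assumptions: gestational age 23-28, literal window, between-subject SD 0.3 or 0.5, effect 1.25- to 3-fold from the 10th to the 90th percentile, individual clearances known without error, no other covariates.

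- Wrong age among runs retaining an age term: about 22-47% at n=10 and 8-44% at n=28.
- Wrong age among all runs: about 2-20%, because often neither passes 6.63.
- Example, n=28, postnatal age true, 1.5-fold effect, SD 0.3: an age term is kept in 54.5% of runs and is wrong in 29.5% of those; 0.545 × 0.295 = 0.161 of all runs. At n=10 the wrong share in this setting is 39%.
- Best case, n=28, 3-fold, SD 0.3: an age term is kept in essentially every run and is wrong in 7.8%.
- Benchmark with two normally distributed covariates (1.5-fold, SD 0.3): the wrong share rises from 10% at r = 0 to 41% at r = -0.94 for n=10, and from 1.6% to 32% for n=28. The excess comes from the collinearity.

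**What the label changes.** The documents give no exponent, so this is an illustration only. From 6 to 12 weeks of postnatal age, an exponent of 0.25, 0.5 or 1 raises clearance by 2^0.25 - 1 = 19%, 2^0.5 - 1 = 41% or 100%. A gestational-age term gives 0% within the same infant.

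**Weight.** To stay in, weight needs R² > 1 - exp(-6.63/n): 0.485 at n=10 and 0.211 at n=28. Take a true proportional effect, log-weight SD 0.2-0.3 and residual log-clearance SD 0.3-0.5 (all assumed). The true R² then runs from 0.04/(0.04 + 0.25) = 0.14 to 0.09/(0.09 + 0.09) = 0.50. At n=10 most of that range lies below the bar. In simulation, weight passes 6.63 in about 10-60% of runs at n=10 and 30-98% at n=28.

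**The case against.** The case against has several sound parts.

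- **No correlation is documented.** Any single value, such as -0.94, needs an assumed gestational-age SD (about 1.6 weeks for that one). Only a range can be defended.
- **A reader might infer that the two ages are one variable and can never be separated.** The documents and the figures do not support this. An infant born at 28 weeks can enter at 3 to 5 weeks of age, and in the simulations the right age is kept more often than the wrong one, increasingly so with more infants.
- **A reader might infer that the screen usually mislabels.** The larger percentages apply only when an age term is retained; over all runs the figure is at most about 20%.
- **A reader might infer that the 60 mg/kg dose rests on the label.** The documents do not say that either age was retained, the dose has no age term, and inside the entry window the two labels predict nearly the same clearance. Group 3 troughs are measured directly.
- **Pre-naming one age does not show which is causal.** True; only the limit on interpretation deals with that.
- **The weight point is a separate issue.** Also true: it concerns low power under a strict criterion, not the collinearity of the ages.

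The planned bootstrap and visual predictive check do not settle the matter. Two covariates that fit almost equally inside the window look almost the same on a predictive check, and the plan does not say that selection is repeated within the bootstrap.

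**Conclusion.** The point holds as a limit on what the covariate model can support. With 10 or 28 infants under this entry rule, the screen cannot reliably attribute an age effect to postnatal rather than gestational age. The risk is to interpretation and to projection beyond 31-33 weeks; no effect on the present dose is shown. Weight also has a fair chance of being dropped when its effect is real, especially at n=10.

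The sizes rest on assumed age spreads, effect sizes and SDs. The stand-in ignores sparse-sampling error and competing covariates, which would be expected to make selection less reliable. The n=28 figures assume that the covariate search is repeated with Group 3 data; Section 6 says only that refinement will be performed. The extrapolation concern rests on the stated purpose of informing a later trial, whose age range is not given.

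**What to change.** In Section 6, for the refinement with Group 3 data:

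1. Put body weight on clearance and volume in the base model with fixed, pre-stated exponents, and remove it from the screen.
2. Screen one pre-named age term, not both.
3. Report the observed correlation between gestational and postnatal age.
4. State that any age effect cannot be attributed to postnatal rather than gestational age and is not to be extrapolated beyond the entry window.

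In a simulation, fixing the weight exponent at 0.75 or 1 gave lower error in predicted clearance than the screen at n=10 for every true exponent tried (0.5 to 1.25), and in most settings at n=28.

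The cost is a few sentences and a model re-run. The downside is that the fixed exponent may be somewhat off and one age term is not tested separately. Sensitivity runs with the exponent estimated and with the other age term would show how much either choice matters.
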